## 1 List of abbreviations and definition of terms

Abbreviation	Definition
ACR	American College of Rheumatology
ADA	Anti-drug antibodies
AE	Adverse event
ATC	Anatomical Therapeutic Chemical Classification System
BMI	Body mass index
CRF	Case report form
CRO	Contract research organization
CRP	C-reactive protein
CSR	Clinical study report
ECG	Electrocardiogram
eCRF	Electronic case report form
eDiary	Electronic diary
eGFR	Estimated glomerular filtration rate
ePRO	Electronic PRO
EQ-5D-5L	EuroQol 5 dimensions 5 levels
EULAR	European League Against Rheumatism
FDA	Food and Drug Administration
GFR	Glomerular filtration rate
HR	Heart rate
HRQL	Health related quality of life
ICF	Informed consent form
ICH	International Council of Harmonization
IL-1Ra	Endogenous interleukin 1 receptor antagonist
IL-6	Interleukin-6
IL-8	Interleukin-8
i.m.	Intramuscular
IMP	Investigational medicinal product
ITT	Intention-to-treat
IWRS	Interactive web response system
LS	Least square
LSM	Least square means
MAR	Missing at random
MCS	Mental component summary
MedDRA	Medical Dictionary for Regulatory Activities
MMRM	Mixed model repeated measures

Abbreviation	Definition
MNAR	Missing not at random
MPO	Myeloperoxidase
NAb	Neutralizing anti-drug antibodies
No.	Number
NSAID	Non-steroidal anti-inflammatory drugs
PCS	Physical component summary
PP	Per-protocol
PRO	Patient reported outcome
PT	Preferred term
SAA	Serum amyloid A
SAE	Serious adverse event
SAP	Statistical analysis plan
s.c.	Subcutaneous
SD	Standard deviation
SDTM	Study data tabulation model
SF-36	Short Form (36) Health Survey (acute, Version 2)
Sobi	Swedish Orphan Biovitrum
SOC	System organ class
SOP	Standard operating procedure
TEAE	Treatment-emergent adverse event
TIA	Transient ischemic attack
ULT	Urate lowering therapy
VAS	Visual analogue scale
WPAI:SHP	Work productivity and activity impairment:specific health problems

## **2 Introduction**

This SAP describes the planned analyses and reporting for the Sobi study Sobi.ANAKIN-401, A randomized, double-blind, active-control, multicenter, efficacy and safety study of 2 dose levels of subcutaneous anakinra compared to intramuscular triamcinolone in the treatment of acute gouty arthritis, followed by an extension period of up to 2 years.

This phase II study is being completed to assess the efficacy and safety of anakinra for the treatment of acute gouty arthritis in patients for whom NSAIDs and colchicine are either contraindicated or not appropriate due to anticipated changes in patient status, not tolerated or do not provide an adequate response.

The purpose of this SAP is to outline the planned analyses to be completed to support the CSR for the study Sobi.ANAKIN-401. The planned analyses identified in this SAP will be included in regulatory submissions and/or future manuscripts. Also, exploratory analyses not necessarily identified in this SAP may be performed to support the clinical development program. Any post-hoc or unplanned analyses not identified in this SAP will be clearly identified in the respective CSR.

The structure and content of this SAP provides sufficient detail to meet the requirements identified by the FDA and International Council of Harmonisation of Technical Requirements for Registration of Pharmaceuticals for Human Use (ICH): Guidance on Statistical Principles in Clinical Trials. All work planned and reported for this SAP will follow internationally accepted guidelines, published by the American Statistical Association and the Royal Statistical Society, for statistical practice.

## **3 Study objectives and endpoints**

### **3.1 Primary objective**

The primary objective of the study is to evaluate the efficacy of anakinra compared to triamcinolone acetonide 40 mg i.m. injection, hereafter referred to as triamcinolone, with respect to patient-assessed pain intensity in the treatment of a gouty arthritis flare (based on patients' first flare treated in the study).

### **3.2 Secondary objectives**

The secondary objectives of the study are:

- To evaluate the primary endpoint and the secondary endpoints supporting primary objective for the 2 different anakinra dose groups compared to triamcinolone in the treatment of the first gouty arthritis flare.
- To evaluate the time to onset of effect, time to response, time to pain resolution, time to rescue medication, physician's assessment of global response and clinical signs, patient's

- assessment of global response, inflammatory biomarkers, and safety of anakinra compared to triamcinolone in the treatment of the first gouty arthritis flare both for the combined anakinra group (100 and 200 mg) and the 2 different anakinra dose groups.
- To evaluate the primary and secondary endpoints and safety of the combined anakinra group (100 and 200 mg), the 2 different anakinra dose groups and triamcinolone in the treatment of subsequent flares. Subsequent flares are flares occurring after the first flare in the study and within 52 weeks of randomization of the last randomized patient in the study. However the extension will be a maximum of 2 years (104 weeks) after randomization for the individual patient in the study.

### **3.2.1 Exploratory objectives**

The exploratory objectives of the study are:

- To evaluate the effect of anakinra compared to triamcinolone on HRQL and health care resource utilization in the treatment of the first gouty arthritis flare.
- To evaluate the effect of anakinra compared to triamcinolone on exploratory inflammatory biomarkers in serum in the treatment of gouty arthritis flares. (Statistical analyses of exploratory inflammatory biomarkers of more exploratory nature will not be described in this SAP and these results may be reported separately).
- To analyze for genetic factors potentially contributing to the patient's response to anakinra, safety and tolerability. Such genetic factors may include genes within the target pathway, or other genes believed to be related to the response to anakinra. The statistical analysis of genetic factors will not be described in this SAP and these results may be reported separately.

## **3.3 Study endpoints**

### **3.3.1 Primary efficacy endpoint and secondary endpoints supporting the primary objective**

#### **3.3.1.1 Primary efficacy endpoint**

The primary efficacy endpoint is:

- The change in patient-assessed pain intensity from baseline to 24 to 72 hours (average of the assessments performed at 24, 48, and 72 hours) for the first flare.

#### **3.3.1.2 Secondary endpoints supporting the primary objective**

The following secondary endpoints will be evaluated to support the primary objective:

- Change from baseline in patient-assessed pain intensity in the index joint as measured by VAS at 6, 12, 18, 24, 36, 48, 72 hours, and Days 5, 6, 7, and 8 for the first flare.

- Change from baseline in patient-assessed pain intensity in the index joint as measured by a 5-point Likert scale at 6, 12, 18, 24, 36, 48, 72 hours, and Days 5, 6, 7, and 8 for the first flare.

### 3.3.2 Secondary efficacy endpoints

The following secondary endpoints will be assessed for the first flare and subsequent flares. All comparisons versus baseline (pre-dose measurement at Visit 1) will be made against the baseline of the first and subsequent flares, respectively.

- Time to onset of effect (defined as  $\geq 20$  % change from baseline pain intensity on VAS).
- Time to response (defined as  $\geq 50$  % change from baseline pain intensity on VAS).
- Response (defined as  $\geq 50$  % change from baseline pain intensity on VAS) at 24, 48 and 72 hours, Day 8 and Day 15 (yes/no).
- Resolution of pain (defined as  $< 10$  mm on VAS) at 72 hours, Day 8 and Day 15 (Yes/No).
- Time to resolution of pain (defined as  $< 10$  mm on VAS).
- Time to intake of rescue medication from first IMP administration.
- Type and number of occasions of intake of rescue medication taken from first IMP administration to Day 8.
- Patient's assessment of global response to treatment (5-point Likert scale) at 72 hours, Day 8 and Day 15.
- Physician's assessment of global response to treatment (5-point Likert scale) at 72 hours, Day 8 and Day 15.
- Physician's assessment of clinical signs at 72 hours, Day 8 and Day 15 in index joint tenderness, swelling and erythema.
- Change from baseline in the inflammatory biomarkers CRP and SAA at 72 hours, Day 8 and Day 15.

Additional assessment for the subsequent flares:

- Change in patient-assessed pain intensity in the index joint as measured by VAS score from baseline to 24 to 72 hours (average of the assessments performed at 24, 48 and 72 hours).
- Change from baseline in patient-assessed pain intensity in the index joint as measured by VAS score at 6, 12, 18, 24, 36, 48, 72 hours and Days 5, 6, 7 and 8.
- Change from baseline in patient-assessed pain intensity in the index joint as measured by a 5-point Likert scale at 6, 12, 18, 24, 36, 48, 72 hours and Days 5, 6, 7 and 8.

### 3.3.3 Safety endpoints

The study has the following safety endpoints:

- Occurrence of AEs.
- Laboratory safety assessments.

- Vital signs .
- Occurrence of ADA against anakinra at Visit 1 (before IMP administration) and at Day 8, Day 15, Day 28 and Week 12 (the assessment at Day 28 and Week 12 will only be performed if no subsequent flare has occurred at that timepoint).

### **3.3.4 Serum concentrations**

The following endpoint will be assessed to evaluate anakinra serum concentrations:

- Serum concentration of IL-1Ra/anakinra at baseline, 72 hours (just before IMP administration) and at Day 8, Day 15, Day 28 and Week 12 (the assessment at Day 28 and Week 12 will only be performed if no subsequent flare has occurred at that timepoint).

### **3.3.5 Exploratory endpoints**

The following exploratory endpoints will be assessed for both the first and subsequent gouty arthritis flares. All comparisons versus baseline (pre-dose measurement at Visit 1) will be made against the baseline of the first and subsequent flares, respectively.

- Change from baseline in health related quality of life (SF-36® Health Survey, acute Version 2) at Day 8 and Day 15.
- Change from baseline in health related quality of life (EQ-5D-5L) at Day 8 and Day 15.
- Work productivity and activity impairment due to a gouty arthritis flare (WPAI:SHP Version 2.0) and health care resource utilization: number of days with hospitalization and number of unscheduled outpatient visits during the last week recorded at Day 8 and Day 15.
- Change from baseline in the exploratory inflammatory biomarkers IL-6, IL-8, calprotectin, neopterin and MPO in serum at 72 hours, Day 15 and Week 12.

## **4 Study methods**

[figure not shown]
### **4.1 Overall study design and plan**

The study consists of 3 periods: an optional pre-screening period, a double-blind treatment period and an extension period.

The treatment period of the first flare is double-blind, and the patients will be randomized to treatment with 100 mg anakinra, 200 mg anakinra or 40 mg triamcinolone acetone in a 1:1:1 ratio. At Visit 1 of each flare, the triamcinolone or matching placebo will be given as one i.m. injection of 1 mL, and at each day of IMP administration period (Days 1 to 5), the anakinra and/or matching placebo will be given as 2 s.c. injections of 0.67 mL.

The double-blind period will be followed by an extension period. During this period, the patients will receive the same treatment for subsequent flares occurring after Day 15 of the latest flare. The extension period will continue for all patients until 52 weeks after randomization of the last randomized patient in the study. However the study treatment of an individual patient's flare will not start later than 2 years (104 weeks) after randomization of that patient. Thus the study will not exceed 104 + 12 weeks for any patient. An overview of the study design is presented in Figure 1.

**Figure 1 Study design**

Abbreviations: FU, Follow-up; N, Number of patients.

At each baseline visit (first and subsequent flares), the joint that is most affected, i.e. most painful, will be defined as the index joint.

The assessment period for each flare will consist of 4 to 6 visits to the study center. The visits are the screening/baseline visit (Visit 1/Day 1), the 72-hour visit (Visit 2/Day 4), the 1-week visit (Visit 3/Day 8), the 2-week visit (Visit 4/Day 15), the 4-week visit (Visit E/Day 28) and the 3 month visit (Visit 5/Week 12). If a subsequent flare has been treated before the Day 28 visit, the Day 28 and Week 12 visits will be cancelled. If a subsequent flare has been treated before a Week 12 visit, that Week 12 visit will be cancelled. Subsequent flares occurring before the Day 15 visit of the latest flare (Visit 4) will be treated with permitted rescue medication, i.e. no IMP will be administered.

A follow-up by phone will be performed at 24 and 48 hours post first IMP administration to remind the patient to complete the assessments and recordings in the eDiary. A follow-up by phone will also be performed every 12 weeks following Visit 5 of the latest flare.

An end-of-study follow-up will be performed either;

1. 52 weeks after randomization of the last patient in the study

or

2. 2 years (104 weeks) after randomization of the individual patient whichever occurs first.

If the IMP treatment started week 40 or later in case 1), or week 92 weeks in case 2), the Week 12 visit will replace the End-of-study follow-up by phone.

All patients will have their follow-up visits/phone calls, irrespective of treatment withdrawal or use of rescue medication.

Subsequent flares occurring before the Day 15 visit of the latest flare (Visit 4) will be treated with permitted rescue medication i.e., no IMP will be administered.

The AE reporting period for all AEs, including SAEs, begins upon receiving the first dose of IMP and ends at Visit E, 28 days after the first dose of IMP. SAEs will also be collected from signing of the ICF until the Week 12 visit (Visit 5). Furthermore, any SAE should be reported irrespective of the time of occurrence if a causal relationship between the event and the IMP(s) is suspected. If the patient is treated with IMP for a subsequent flare, the AE (including SAE) reporting period starts again when the first dose is administered.

Patients who have difficulty in tolerating their pain are allowed to take rescue medication after the 24-hour post-dose pain assessment but not within 6 hours before the 48- and 72-hour post-dose pain assessments. Permitted rescue medication includes topical ice/cold packs, paracetamol/acetaminophen (up to 1000 mg 4 times daily) and/or codeine (up to 50 mg 4 times daily) or short-acting tramadol (up to 100 mg 4 times daily).

Patients still having insufficient relief with the rescue medication listed above after the 72-hour post-dose pain assessment are allowed to take oral prednisone or prednisolone at a dose up to 0.5 mg/kg per day for a maximum of 5 days.

When all patients have conducted the Day 15 visit of the first flare (Visit 4), the database will be locked and the main efficacy analysis will be conducted. The main efficacy analysis includes primarily the statistical analysis of all efficacy endpoints for the first flare. A second database lock will be conducted when all patients have completed the study.

## 4.2 Selection of study population

This study is designed to evaluate the efficacy and safety of anakinra in the treatment of gouty arthritis flares in adult male and female patients for whom NSAIDs and colchicine are either contraindicated or not appropriate due to anticipated changes in patient status, not tolerated or do not provide an adequate response. To ensure a reliable diagnosis of gouty arthritis, patients to be included in the study must meet the ACR/EULAR 2015 gout classification criteria (**Error! Reference source not found.**).

A history of  $\geq 1$  self-reported flare of gouty arthritis during the previous 12 months is required for inclusion in the study to ensure that the patients have an active gouty arthritis.

To ensure that a significant number of subsequent flares are treated in the study, the extension period will continue for all patients until 52 weeks after randomization of the last randomized

patient in the study or a maximum of 104 weeks after randomization of the individual patient in the study.

To be included, patients must have a patient-reported current ongoing flare of gouty arthritis characterized by baseline pain intensity in the index joint of  $\geq 50$  on a 0 to 100 VAS, as well as currently tender ( $\geq 1$  on a 0-4-point Likert scale) and swollen ( $\geq 1$  on a 0-4-point Likert scale). The onset of the current ongoing flare should be within 4 days prior to randomization.

Further, if the patient is on urate-lowering therapy, a stable dose and regimen for at least 2 weeks prior to randomization and expectance to remain on a stable dose and regimen for  $\geq 2$  weeks after administration of the first dose of study treatment is required.

Complete details of the patient inclusion and exclusion criteria are provided in [CSP Section 7.3.1](#) and [CSP Section 7.3.2](#).

Patients with data collection failure for primary endpoint are defined as patients who are randomized in the clinical study but have no values collected for patient-assessed pain intensity from baseline to 72 hours for the first flare. These patients will however continue in the study and be included in the ITT and safety populations. For each primary endpoint collection failures, one extra patient can be randomized in the study. Maximum 10 extra patients can be randomized under this protocol.

### **4.3 Method of treatment assignment and randomization**

Up to totally 169 patients can be randomized in the study. Initially 159 patients will be randomized, 53 to triamcinolone and 106 to anakinra (53 to 100 mg and 53 to 200 mg). As described in Section 7, up to a maximum of 10 extra patients can be randomized. Patients will be randomized to treatment with anakinra 100 mg, anakinra 200 mg or triamcinolone 40 mg in a 1:1:1 ratio. The randomization will be stratified by ULT use (yes/no) and BMI ( $< 30.0$  or  $\geq 30.0$  kg/m^2) at inclusion.

For subsequent flares during the extension period, patients will continue to receive the same treatment with anakinra 100 mg, anakinra 200 mg or triamcinolone 40 mg.

An IWRS will be used for the randomization. Biostatistics at Perceptive will generate the randomization scheme for the IWRS, which will link sequential patient randomization numbers to treatment codes.

The randomization numbers will be generated in blocks. Within each block, equal numbers of patients will be allocated to each treatment group. The block size will not be revealed to any personnel involved in the study except the lead statistician at PRA and the study statistician at Sobi before breaking of the blind.

The first part of the study, i.e. treatment and follow-up of the patients' first flare, is double-blind. Treatment assignment will be blinded for the patients, the investigators and any personnel involved with the study conduct or evaluation at the investigational sites, CRO and sponsor.

Until all patients have completed the Day 15 visit of the first flare (Visit 4), the randomization scheme will only be disclosed to selected CRO personnel to ensure correct packaging of the IMP and correct set-up of the IWRS. The disclosure of the randomization scheme and any individual patient's treatment assignment will be protected by the SOPs of the CRO.

When all patients have completed the Day 15 visit of the first flare, a first database lock will be performed and the main efficacy analysis will be conducted (see Section 6.1). An independent unblinded programmer at the CRO will create unblinded SDTMs to be sent to Sponsor. Blinding will be maintained for patients, investigators, site staff, CRO and applicable vendors throughout the extension phase to prevent any bias in data handling. The Sponsor will take no part in the operational conduct of the study after the first database lock. Details of this process will be outlined in the "Process guideline for data integrity protection after database lock 1".

Unblinding, i.e. breaking the code for an individual patient during the study, is restricted to emergency situations and should only be used under circumstances where knowledge of the treatment is necessary for the proper handling of the patient. The decision to break the code must be made by the investigator. Unblinding should be documented according to instructions in the IWRS manual. The study monitor and sponsor must as soon as possible be informed about the code break.

## **5 Changes from protocol affecting the statistical analysis**

According to the protocol, AEs and SAEs will be classified as occurring during ADA presence when the starting date for the AE is within the time period after the latest negative assessment until next negative assessment with a positive assessment of ADA in between. Instead AEs and SAEs will be presented by ADA positive and ADA negative patients for the whole study period.

The relationship between ADA and efficacy and the relationship between ADA and IL-Ra/anakinra concentrations over time will also be explored which was not described in the protocol.

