7.3.3 Withdrawal of patients from treatment or study

7.3.3.1 Withdrawal from study treatment

A patient should be withdrawn from the study treatment if, in the opinion of the investigator, it is medically necessary, or if it is the wish of the patient.

When a patient is withdrawn from treatment, the date of the last IMP administration and the date and reason for treatment withdrawal should be clearly described in the relevant sections of the electronic case report form (eCRF). If a patient is removed from treatment because of an adverse event (AE), the reason for treatment withdrawal should always be stated as ‘adverse event’ irrespective of whether this was the investigator’s or the patient’s decision.

If a patient has been withdrawn from study treatment of one flare but fulfils the eligibility criteria for a subsequent flare, study treatment can be re-initiated. However, this is not applicable if the withdrawal from study treatment was due to a safety concern related to the IMP treatment, as judged by the investigator, see below (7.3.3.2).

All patients will continue to participate in the study and should be followed and assessed according to the protocol until the End of study follow-up call even if study treatment is discontinued unless consent is withdrawn or the patient is lost to follow-up.

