9.3.6 Analysis of safety and tolerability data

Safety tabulations will be performed with respect to adverse event data, clinical laboratory results and vital sign data. Continuous variables will be summarized using the number of patients, the mean, the standard deviation, the median, the minimum value, and the maximum value. Categorical variables will be summarized using frequency counts and percentages. No statistical hypothesis tests will be performed.

All data will be displayed in individual patient data listings.

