## **10 Patient disposition**

All patient disposition data will be presented by triamcinolone, the combined anakinra group, anakinra 100 mg/day, anakinra 200 mg/day and overall.

The number and percentage of patients who were randomized, initiated treatment, completed and discontinued study together with the reasons for discontinuations will be presented both for each treated flare and for the full study. If a patient prematurely discontinues the study during a flare, all prior flares are completed (i.e. only the last flare may be prematurely discontinued). If the discontinuation is after the Day 15 visit, the flare is considered completed (i.e. all flares may be completed even if the patient has prematurely discontinued the study). Otherwise, the patient has prematurely discontinued the flare with the reason for discontinuation the same as the reason for premature discontinuation of the study.

The number of weeks in the study and the number of treated flares experienced by the patients during the study will be presented by descriptive statistics for the ITT and safety population. Further, the number and percentage of patients experiencing 1 treated flare, 2 treated flares, 3 treated flares, etc. will also be presented for the ITT and safety population.

The total number and percentage of patients who completed treatment and discontinued treatment together with reason for discontinuation will be tabulated for each flare and overall for the safety population.

The number and percentage of patients in each strata will be presented for the ITT, PP and safety populations. Stratification data will be received from the IWRS system and actual strata will be derived using CRF data.

The distribution of patients at each site will be tabulated for the ITT population, sorted by descending number of patients.

A table displaying the number and percentage of patients with each type of major protocol deviations that lead to exclusion from the PP population will be presented. Percentages will be based on the ITT population.

The number and percentage of patients in the ITT population, the PP population and the safety population will be presented.

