### **16.6.1 Presence of anti-drug antibodies**

The number and proportion of patients with presence of ADA (treatment induced, treatment boosted or treatment unaffected), NAb and cross-reactivity at baseline, Day 8, Day 15, Day 28 and Week 12 will be summarized for each flare.

For patients with presence of ADA, the ADA titers at baseline, Day 8, Day 15, Day 28 and Week 12 will be summarized by descriptive statistics for each flare. Depending on how the results are reported, ADA titers might be categorized as eg. low (<50), medium (>50 and <500) or high (>500).

The cumulative number and proportion of ADA positive and ADA negative subjects will also be summarized by flare over the study.

The number and proportion of transient ADA positive patients, persistent ADA positive patients and off-treatment persistent ADA positive patients will be summarized for the whole study,

The number of patients with occurrence of transient and persistent ADA during the study will be presented graphically.

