### **16.6.2 Anti-drug antibodies versus safety**

AEs and SAEs will be presented by ADA positive and ADA negative patients for the whole study period by SOC and PT. ADA positive patients will then be further categorized in:

1. Transient ADA positive patients.
2. Persistent ADA positive patients.

SAEs will be listed together with the ADA titer for the positive ADA sample taken closest before and after the start of the event.

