### **16.6.3 Anti-drug antibodies versus efficacy**

The mean pain intensity on VAS at each timepoint up to Day 8 will be presented by ADA presence and by NAb presence by descriptive statistics and in graphs as applicable. The presentations will be repeated for each subsequent flare. ADA presence will be defined as being ADA positive at least once at Day 1 or Day 8; no ADA presence will be defined as being negative at both Day 1 and Day 8. Undetermined ADA presence is defined as both assessments are missing or if one assessment is negative and the other is missing.

For subsequent flares, the ADA titer at Day 1 will be plotted against VAS at 72 hours.

For baseline, Day 8 and Day 15, CRP and SAA will be presented by ADA presence and by NAb presence. The presentations will be repeated for each subsequent flare. ADA presence will be defined as being ADA positive at least once at Day 1, Day 8 or Day 15; no ADA presence will be defined as being negative at both Day 1, Day 8 and Day 15. Undetermined ADA presence is defined as all assessments are missing or if 1 or 2 assessments are negative and the other assessments are missing.

For subsequent flares the ADA titer will be plotted against CRP and SAA at Day 1, Day 8 and Day 15.

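### The adverse event table by ever/never ADA status ignores the number of treated flares, so it can show more events in ADA-positive patients when no association exists

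*SAP*

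**What the plan says.** Protocol 9.3.4.11 places an event in a period of ADA presence according to its start date, using the negative and positive samples around it. SAP section 5 openly replaces that rule, without giving a reason: "Instead AEs and SAEs will be presented by ADA positive and ADA negative patients for the whole study period". SAP 16.6.2 sets out the replacement: "AEs and SAEs will be presented by ADA positive and ADA negative patients for the whole study period by SOC and PT". Under SAP 18.26 one treatment-induced or treatment-boosted positive sample at any time makes a patient ADA positive, so the status is ever/never.

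Protocol 7.5.6.5 schedules ADA samples before the first dose and at Day 8, Day 15, Day 28 and Week 12 of each flare; the last two are dropped if a new flare intervenes. Protocol 7.5.6.1.2 restarts adverse event reporting at the first dose of each treated flare.

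Several related outputs are planned:

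- SAP 16.6.2, serious events only: "SAEs will be listed together with the ADA titer for the positive ADA sample taken closest before and after the start of the event".
- SAP 16.6.3, repeated for each subsequent flare: "The mean pain intensity on VAS at each timepoint up to Day 8 will be presented by ADA presence and by NAb presence". CRP and SAA are handled in a similar way.
- SAP 16.6.1: "The cumulative number and proportion of ADA positive and ADA negative subjects will also be summarized by flare over the study".
- SAP 10: "the number of treated flares experienced by the patients during the study will be presented by descriptive statistics for the ITT and safety population".
- SAP 16.2: length of the reporting period, and event tables by flare, neither split by ADA status.
- Protocol 9.3.6: "All data will be displayed in individual patient data listings".

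None of these summarizes adverse events by ADA status per flare.

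**The concern.** The number of treated flares drives both sides of the table. It raises the chance of ever testing positive and the chance of ever reporting an event, so the two can look associated when they are not.

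A second, separate issue is timing. In the first flare the earliest post-dose sample is Day 8, after all five dosing days. An event on Days 1 to 5 of that flare therefore precedes any possible treatment-induced positive sample, yet it counts under ADA positive if the patient converts later.

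This matters because Protocol 7.2.1 gives safety and immunogenicity as the main aim of the extension. Protocol 5.3 names allergic or anaphylactic reactions, injection-site reactions and reduced efficacy as the possible consequences of ADA under intermittent treatment. A reader of the planned table cannot tell an antibody effect from more treatment courses, or events before antibodies from events after them.

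**Working it through.** The plan states no figure on this point. The schedule gives exact counts; everything after step 1 rests on assumed rates.

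**1. Opportunity by number of treated flares, k** (Protocol 7.5.6.5, 7.5.6.1.2; re-treatment not within 14 days, 7.3.2).

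- ADA samples after the first dose: 4k + (k − 1) if every flare runs to Week 12; 2(k − 1) + 4 + (k − 1) if each next flare is treated before Day 28.
- Days of non-serious event reporting: 28k, or 14(k − 1) + 28.

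| k | ADA samples after first dose | Reporting days |
|---|---|---|
| 1 | 4 | 28 |
| 3 | 10 to 14 | 56 to 84 |

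**2. Null model.** Let a be the event probability per flare and p the per-flare probability of a first positive sample, independent of each other. For a patient with F treated flares, P(any event) = 1 − (1 − a)^F and P(ever positive) = 1 − (1 − p)^F.

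*Equal flare counts.* With F = 3 for everyone and a = 0.2, both ADA groups have event risk 1 − 0.8³ = 0.488, so the ratio is 1.00. Pre-positive events are still counted under ADA positive here, which shows that timing alone creates no excess.

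*Unequal flare counts.* Assume 45/20/15/10/10% of patients have 1/2/3/4/6 treated flares, with a = 0.2 and p = 0.1.

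- P(ever positive) = 0.45(0.100) + 0.20(0.190) + 0.15(0.271) + 0.10(0.344) + 0.10(0.469) = 0.205.
- Any event among ADA positive: [0.045(0.200) + 0.038(0.360) + 0.0407(0.488) + 0.0344(0.590) + 0.0469(0.738)] / 0.205 = 0.0974 / 0.205 = 47.5%.
- Any event among ADA negative: [0.405(0.200) + 0.162(0.360) + 0.109(0.488) + 0.0656(0.590) + 0.0531(0.738)] / 0.795 = 0.271 / 0.795 = 34.0%.
- Ratio 47.5 / 34.0 = 1.40. Mean treated flares are 3.23 against 2.06.

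**3. Range for the planned table, no true association.** Simulated with a mean of 1.5 to 3 treated flares, p of 5 or 15% and a of 20 or 40%:

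| Assumption | Ever/never risk ratio |
|---|---|
| Constant event risk, no withdrawal | 1.11 to 1.49 |
| Constant risk, 20% of flares with an event end participation | 1.07 to 1.37 |
| Constant risk, 50% end participation | 1.01 to 1.21 |
| Risk falls 30% per flare, 30% end participation | 0.98 to 1.10 |

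Under constant risk, 20 to 37% of the flares with an event in ADA-positive patients come before the flare of seroconversion. A deliberately wide flare distribution (10% of patients with ten treated flares) takes the ratio up to 1.75.

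**4. Candidate replacements under the same null.**

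- Rate per flare pooled over flare number: 0.99 to 1.02 if risk is constant, but 0.63 to 0.92 if risk falls 30% per flare and 1.09 to 1.57 if it rises 30% (no withdrawal).
- Splitting the conversion flare at the positive sample without person-time, stratified by flare number, constant risk: 0.85 to 0.99 if a quarter of that flare's events precede the sample, 0.66 to 0.83 if half do.
- Classifying each flare by ADA status before its first dose, stratified by flare number: 0.97 to 1.03.

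In these simulations event risk depends only on flare number, so the last result is expected. It shows that the layout adds no bias of its own, not that every other confounder is removed.

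**The case against.** The strongest reply is that this is an untested descriptive table in an exploratory phase 2 trial, the change is declared, and the protocol's own rule had no denominator either. All of that stands: error control is unaffected, and restoring the protocol rule would not remove the dependence on flare count.

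An excess is also not assured. After withdrawal from treatment the protocol lets it restart at a later flare, but "this is not applicable if the withdrawal from study treatment was due to a safety concern related to the IMP treatment", and Protocol 7.3.3.2 takes such patients out of the study after Visit E. Patients with events may then have fewer later flares and fewer ADA samples, which pulls the ratio down.

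Much is already planned, including the titer listing for serious events. That listing helps with timing for those events only. Other events can be related to ADA results only patient by patient through listings.

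A reader might infer that counting pre-positive events inflates the ratio. Step 2 shows it does not. A reader might also infer that a pooled per-flare rate is always wrong; it is adequate if event risk is constant across flares. Protocol 5.1.4.2 reports no rise in event rates in long-term studies, but also says repeated short-term administration has not been studied.

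**Conclusion.** The concern holds, limited to interpretation. The ever/never table can show a spurious excess of events in ADA-positive patients, caused by unequal numbers of treated flares and absent when flare counts are equal. The inclusion of events before the first positive sample is a separate misclassification of timing.

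The size is unknown. Under the assumed rates the null ratio runs from about 1.0 (nearly all patients with one treated flare, or event risk falling across flares together with event-related withdrawal) to about 1.5. Precision will be low: with 106 anakinra patients the assumed rates give about 8 to 39 ADA-positive patients, and 23 of 24 approximate 95% intervals for the crude ratio (constant risk, no withdrawal) include 1.0.

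The documents do not support saying that the table will show an excess, that ADA-positive patients will be few (no ADA rate is given), or that the change was undisclosed.

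**What to change.** Keep the ever/never table and add one adverse event table for anakinra patients, combined and by dose, by treated flare:

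- Classify each flare by ADA status before its first dose: any earlier treatment-induced or boosted positive sample, including that flare's pre-dose sample, versus none.
- Show the flare in which a patient first becomes positive as its own row. Do not split its events at the positive sample without person-time, because that biases the comparison the other way.
- Stratify by flare number rather than relying on a rate pooled over flares.
- Show treated flares and reporting time by ADA status alongside.

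The data are already collected, SAP 18.24 links each event to a flare, and SAP 6.2 allows documented updates before the final lock. The cost is one extra table with small cells, especially at later flares. It offers no comparison at flare 1, and seroconversion is known only to the sampling interval.

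Two separate minor wording items in SAP 18.26 can be settled in the same update. First, a patient who is only treatment-boosted, or who is positive at the last sample without two sequential positives, is neither transient nor persistent. Second, the off-treatment class needs a sample at least 16 weeks after the last dose, but Week 12 (Day 85) is only 80/7 = 11.4 weeks after the Day 5 dose, so only a later flare's samples can supply it.
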